4 STUDY POPULATION

4.1 Study Population

Study will enroll 139 male and female subjects that meet all protocol defined eligibility criteria.

The period from Screening to completion of active treatment will be approximately 5 days. Patients will be required to have follow up physical examination and laboratory evaluations 7-14 days post-is continuation from study drug.

4.2 Sample Size Considerations

A total of 139 enrolled patents is considered sufficient to show the effect of the Legalon® SIL in preventing liver transplantation, and/or death resulting from amatoxin poisoning.

4.3 Inclusion and Exclusion Criteria

4.3.1 Inclusion Criteria

Subjects' eligibility should be reviewed and documented by the Investigator or a qualified designee before subjects are included in the study.

Subjects must meet all the following inclusion criteria to be eligible for enrolment into the study:

1. Signed Informed Consent(s) for Clinical Trial participation
2. History of eating foraged mushrooms
3. Gastrointestinal symptoms consistent with amatoxin poisoning (cramping abdominal pain, nausea, vomiting, and / or watery diarrhea) usually 24-48 hours after mushroom ingestion
4. Liver function tests consistent with amatoxin poisoning: AST or ALT above the institutions upper limit of normal after mushroom ingestion

4.3.2 Exclusion Criteria

Subjects must not be enrolled in the study if they meet any of the following criteria:

1. Evidence of significant medical illness or any other abnormal laboratory finding that, in the Investigator's judgment, will substantially increase the risk associated with the patient's participation in, and completion of, the study, or could preclude the evaluation of the patient's response.

Note: There are no adequate data from the use of Legalon® SIL in pregnant women and for this reason Legalon® SIL administration during pregnancy and lactation is not recommended. Based on the isolated report of fetal toxicity, it is recommended that the risks and benefits of Legalon® SIL therapy should be discussed with pregnant patients prior to use. In pregnant patients with a questionable exposure to amatoxin poisoning, it may therefore be reasonable to monitor carefully serial liver enzyme tests (e.g. every 4 hours) and defer initiation of Legalon® SIL until abnormalities are detected.

4.3.3 Randomization Criteria

This is an open label study and therefore randomization will not occur.

4.3.4 Criteria for study drug termination, withdrawal from the study and study termination

Subjects will be free to request termination of study drug or withdrawal from the study at any time for any reason.

Subjects must be withdrawn from the study prior to initiating treatment under the following circumstances:

- Laboratory values indicative of recovery prior to the start of Legalon® SIL

A subject must terminate study drug for safety reasons under the following circumstances:

- Development of a SAEs that is deemed attributable to Legalon® SIL by the OSI

A subject may be required to terminate study drug for other reasons including the following:

- Patients in whom, after 96 hours of starting treatment there is no significant improvement in the PT/INR and transaminases, termination of treatment may occur following consultation between the OSI and PPI.
- If it is in the subject's best interest based on decision of the OSI or his/her Sub-Investigator e.g. due to occurrence of an AE and/or other findings considered to present a safety concern to continued dosing with study drug.
- Despite education/reinforcement, the subject shows persistent inadequate compliance with required procedures, potentially compromising safety monitoring while on study drug.

Unless consent is withdrawn, subjects who prematurely terminate study drug and are discharged from the hospital, will have PT/INR, liver transaminases collected by local lab and have a physical examination performed by local physician 10 days post last dose of study drug. The OSI is responsible for obtaining the results of these procedures from the patient.

The Principal Investigator and/or Mylan reserves the right to terminate the study for any reason.

The study will be terminated early if there are significant safety concerns.

4.3.5 Females - Childbearing Potential

4.4 If the patient is pregnant appropriate counseling will be provided based on the risk/benefit condition. Pregnancy Testing

Serum or urinary pregnancy testing will be performed on all females of childbearing potential as described in the schedule of activities. In the event of a positive test, the patient will be informed that systematic data on the use of SIL in pregnancy and lactation are not available.

Note: There are no adequate data from the use of Legalon® SIL in pregnant women and for this reason Legalon® SIL administration during pregnancy and lactation is not recommended. Based on the isolated report of fetal toxicity, it is recommended that the risks and benefits of Legalon® SIL therapy should be discussed with pregnant patients prior to use. In pregnant patients with a questionable exposure to amatoxin poisoning, it may therefore be reasonable to monitor carefully serial liver enzyme tests (e.g. every 4 hours) and defer initiation of Legalon® SIL until abnormalities are detected. Any patient found to be pregnant at time of initiation of treatment, the pregnancy will be followed up and reported to the sponsor as per Section 9.2.6.

5 STUDY DRUG

5.1 Investigational Drug

Legalon® SIL is a fully developed and documented pharmaceutical formulation manufactured by Madaus (Cologne, Germany). Its active ingredient is silibinin-C-2',3-dihydrogen succinate, disodium salt Fig. (1). It has the molecular formula C₃₃H₂₈O₁₆Na₂ and a molecular mass of 726.56 g/mol. It is a microcrystalline powder that results from the esterification of silibinin with succinic anhydride to form its hydrosoluble disuccinic acid ester for parenteral application. Silibinin, a flavonolignan obtained by extraction of the seeds from milk thistle fruit (Ph. Eur.), is a mixture of two diastereomers, commonly named silibinin A and silibinin B. After the reaction of silibinin with succinic anhydride, silibinin-C-2',3-dihydrogen succinate, disodium salt is obtained as a mixture of cis- and trans diastereomers of silibinin A and B dihydrogen succinates. Legalon® SIL is currently registered and/or licensed in over a dozen European countries specifically for the treatment of *Amanita phalloides* intoxication.

Legalon® SIL

The drug is provided in carton containing four, rubber-stoppered vials. Each vial contains 528.5 mg of (equivalent to 350 mg of silibinin) powder for solution for infusion.

One vial contains:

Drug substance

Silibinin-C-2',3-dihydrogen succinate, disodium salt, 528.5 mg
[corresponding to 476 mg mono-, dihydrogensuccinate sodium salts (HPLC)]
equivalent to 350 mg (315 mg HPLC) of silibinin

Excipients

Inulin 70 mg USP
Nitrogen (as inert gas) Ph.Eur.
Total sum: 598.5 mg
Manufacturer: Madaus GmbH, Cologne (Germany)

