| | 
More than 90% of all fatal mushroom poisonings worldwide are due to amatoxin containing species that grow abundantly in Europe, South Asia, and the Indian subcontinent. Many cases have also been reported in North America (1,2,3). Initial symptoms of abdominal cramps, vomiting, and a severe cholera-like diarrhea generally do not manifest until at least six to eight hours following ingestion and can be followed by renal and hepatic failure. Outcomes range from complete recovery to fulminant organ failure and death which can sometimes be averted by liver transplant.
 
Epidemiological data on mushroom poisoning, particularly poisoning with amatoxin-containing mushrooms, are rare. The true incidence of this intoxication is unknown since national data banks maintained at poison control centers have only incomplete data of this non-reportable illness [4].
 
Uncontrolled European studies and emergency use in the USA, suggest that treatment of amatoxin poisoning with Legalon® SIL drug may prevent severe morbidity (hepatic failure) and mortality.
 
This is a Phase II Multi-Center Open-Label Clinical Trial to Assess the Prevention of Liver Transplantation and/or Death Among Subjects Treated with Intravenous Silibinin (Legalon® SIL) for Amatoxin Induced Hepatic Failure. A total of 139 subjects will be enrolled into this study.
 
Legalon® SIL is formulated as a sterile lyophilisate in rubber-stoppered vials to be dissolved for intravenous infusion, containing 528.5 mg silibinin-C-2',3-dihydrogen succinate, disodium salt which is equivalent to 350 mg of silibinin according to DNPH testing or 315 mg of silibinin according to HPLC determination. The recommended daily dose is 20 mg silibinin/kg via continuous infusion over 24 hours, following a single loading dose of 5 mg silibinin/kg on the first day of treatment.
 
Subjects will be screened for eligibility and, if confirmed to meet the study criteria, will be enrolled to receive treatment of Legalon® SIL.
 
The study is comprised of a screening period of up to 24 hours from the time a potential study participant is identified. Treatment may be administered for up to 96 hours, or longer, following consultation with PPI. The final study assessment (Follow-up Visit) is to occur at 10 (+/-2) days from the last administered treatment. During screening, treatment and follow-up, assessments for medical history (only at screening), vital signs, labs and physical examination will be completed. Concomitant medications and adverse events will be recorded on every subject from the time of consent through the completion of the Follow-up Visit. Sponsor should be notified of any SAEs reported to the site and up to 30 days after discontinuation of study medication.
 |

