| 
Methodology and treatments
 | 
Legalon® SIL will be administered to subjects with amatoxin poisoning diagnosed by medical history, gastrointestinal symptoms, elevated liver enzymes (values higher than the upper limit of institution’s normal for the age/sex at screening). Treatment consists of a 5 mg/kg loading dose followed by 20 mg/kg/day via continuous infusion (13). The treating physician is expected to administer supportive therapy of his/her choosing but consistent with best practices. Other measures to eliminate residual toxin, maintain perfusion and vital signs, and prevent coagulopathy will be as chosen by the treating physician.
 
Legalon® SIL will be discontinued when prothrombin time and/or INR have returned to normal range, and when transaminases (AST and ALT) both are no more than 2 times the upper limit normal for the institution.
 
If treatment is approaching 96 hours and the above criteria for discontinuation have not been met, the Primary Principal Investigator (PPI) and Onsite Investigator (OSI) must discuss the viability of continued study treatment. Upon confirmation of eligibility, subjects will receive a loading dose of 5 mg/kg of Legalon SIL intravenously (IV) over 1 hour via an infusion pump followed by 20 mg/kg continuous IV over 24 hours.
 
Upon discharge from hospital, the subject should be advised to be seen for a physical examination and blood work (transaminases and PT/INR) approximately 10 days post discharge. The OSI or his designee is responsible to follow up with the subject for these results.
 
The Protocol requires that the OSI and the PPI engage in daily telephone consultations once the subject is enrolled and for the duration of treatment with the study drug. All consultations will be documented and maintained on file by the PPI and OSI.
 |

| | |

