1 STUDY SCHEDULE OF ACTIVITIES

The Schedule of Activities table provides an overview of the protocol visits and procedures. Refer to the Study Conduct Section (6) for detailed information on each procedure and assessment required for compliance with the protocol.

Table 1 Study Schedule

Schedule of Events

| PHASE | SCREENING PHASE | | Dosing | TREATMENT PHASE | | FOLLOW-UP PHASE |
|------------------------------|----------------------------|------------------|--------|---------------------------------------------------------------------------|---------------------------------------------|-----------------|
| | Screening/ Presentation | Pre -First dose* | | Every 6 hours post first dose until discharge or as indicated (+/-1 hour) | Every 24 hours post first dose (+/-2 hours) | |
| Informed consent | X | | | | | |
| History | X | | | | | |
| Physical/ Review of Systems | X | X | | | X | X |
| Vital Signs | X | X | X | | | X |
| CBC, Differential, Platelets | X | X | X | | | |
| Transaminases (AST, ALT) | X | X | X | | | X |
| ALP | X | X | X | | | X |
| Ammonia | X | X | X | | X | X |
| Lactate | X | X | X | | | |
| Amylase | X | X | X | | | X |
| Lipase | X | X | X | | | X |
| Bilirubin (total) | X | X | X | | X | X |
| PT | X | X | X | | X | X |

| PHASE | SCREENING PHASE | | TREATMENT PHASE | | | FOLLOW-UP PHASE |
|--------------------------------------------------------------------------------------------------------------------------|----------------------------|------------------|-----------------|---------------------------------------------------------------------------|---------------------------------------------|-------------------------------------------------------------|
| | Screening/ Presentation | Pre -First dose* | Dosing | Every 6 hours post first dose until discharge or as indicated (+/-1 hour) | Every 24 hours post first dose (+/-2 hours) | |
| Event | | | | | | At Follow-up, 10 (+/- 2) Days after study drug discontinued |
| INR | X | X | | X | | X |
| BUN, Creatinine, GFR | X | X | | X | X | |
| Glucose | X | X | | X** | X | |
| Electrolytes (NA, K, Cl, CO2) | X | X | | X | | |
| Serum Pregnancy test for woman of child bearing potential | X | | | | | |
| Loading dose Legalon-SIL 5mg/kg IV over 1 hour followed by continuous IV infusion of 20 mg silibinin/kg over 24 hours | | | X | | | |
| Adverse Events | X | X | X | X | X | X |
| Concomitant Medications | X | X | X | X | X | X |

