5.1.1 Administration of Study Drugs

Preparation of infusion fluid

- Dissolve each of the 4 vials that are contained in a carton with 35 mL of 5% Dextrose or 0.9% sodium chloride solution. Upon reconstitution a total of 140 ml will be available across 4 vials.
- Remove 140 ml from a 500 mL IV container of Dextrose and replace with the 140 ml of reconstituted drug solution
- The initial loading dose is 5 mg/kg for one hour via infusion pump
- After the loading dose, 20 mg/kg/day is infused continuously via infusion pump

In the event of any significant dosing errors, the PPI and Mylan should be contacted immediately.

Since Legalon® SIL is potentially life-saving, reduction or elimination of dosing is to be avoided unless there is strong reason to think that an adverse event is due to Legalon® SIL, is clinically significant, and cannot be managed otherwise.

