9.2.5 Special Situations

Emergency Room Visits: Post discharge from the hospital and up to 30 days post discontinuation of study drug, events that result in emergency room visits that do not result in admission to the hospital are not routinely considered to be serious events; however, these events should be evaluated for one of the other serious outcomes (e.g., life-threatening, other serious [medically significant] events).

Neoplasms: For this protocol, any diagnosis of cancer or neoplasm is considered serious (significant medical event criterion).

Quality Complaints: Quality complaints related to study drug are not AEs, however, any AE or SAE experienced by the subject as a result of these should be documented in the CRF and SAEs sent to Mylan on the SAE reporting form. Please see Section 5.3 for further details.

Overdose: The protocol specified dose should not be exceeded. Overdose will be documented as a deviation in the source and communicated to the sponsor Clinical Scientist or designee. The subject should be monitored appropriately by the investigator for latent adverse effects. Any adverse event occurring as a result of overdose or medication error will be recorded as an AE in the CRF and if serious (per definition, Section 9.2.1) reported immediately to sponsor as per Section 9.2.7. Please see Section **Error! Reference source not found.** for further details.

9.2.6 Exposure to Investigational Drug During Pregnancy:

Pregnancy in a female subject is to be reported on the Pregnancy Report Form within 24 hours of awareness starting from first dose of study medication. The pregnancy should be followed to term or termination and updates submitted during the pregnancy at 3-monthly intervals via the Pregnancy Report Form.

While pregnancy itself is not considered an AE or SAE, any pregnancy complication or elective termination of pregnancy for medical reasons will be recorded as an AE or a SAE depending upon the Investigator's medical judgment.

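### The protocol does not fix the substance behind its mg/kg doses or the vial content used to convert them, so the volume or pump rate for the same written dose is not determined

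*Combined protocol and SAP*

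**What the plan says.** The dose is written in three ways.

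- **As silibinin.** Synopsis, Background and Rationale: "The recommended daily dose is 20 mg silibinin/kg via continuous infusion over 24 hours, following a single loading dose of 5 mg silibinin/kg".
- **As the product, for the loading dose.** Synopsis, Methodology and treatments: "loading dose of 5 mg/kg of Legalon SIL intravenously (IV) over 1 hour via an infusion pump followed by 20 mg/kg continuous IV". Here the 20 mg/kg that follows carries no substance of its own. Table 1 puts the product name on the loading dose and silibinin on the infusion in a single row: "Loading dose Legalon-SIL 5mg/kg IV over 1 hour followed by continuous IV infusion of 20 mg silibinin/kg over 24 hours".
- **With no substance.** The summary paragraph of Section 2.2 gives 5 mg/kg and 20 mg/kg/day. Section 5.1.1, the preparation section, does the same: "After the loading dose, 20 mg/kg/day is infused continuously via infusion pump".

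Section 5.1 gives the vial content as 528.5 mg of the disodium salt, 476 mg of the succinate salts by HPLC, and "equivalent to 350 mg (315 mg HPLC) of silibinin". The synopsis identifies the 350 mg figure as the DNPH result.

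Section 5.1.1 fixes the bag: four vials, each dissolved in 35 mL, replace 140 mL in a 500 mL container. It gives no mg/mL for the result. Section 9.2.5 then says "The protocol specified dose should not be exceeded", and Section 5.1.1 asks for immediate contact about significant dosing errors.

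**The concern.** To set a pump, a site must turn mg/kg into mL. That takes two facts: which substance the mg refers to, and how many mg of it a vial holds. The protocol gives several candidates for the second and is not uniform on the first. A site that takes the synopsis methodology literally could run a different loading volume from one that follows the synopsis background.

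The written text matters more here than in most trials. Section 5.2 expects most physicians to come in without prior ethics approval of the protocol. Section 6.3 wants treatment started as soon as possible once drug arrives, while Section 6.1 allows training up to 24 hours after enrolment. The list of documents sent to the site in Section 6.1 includes the protocol but no pharmacy manual or dosing worksheet.

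Three things are at stake: consistent exposure between sites, a fixed reference for the overdose and dosing-error rules, and a fixed reference for the compliance summary in Section 7.5.1 and for any dose-based deviation that removes a subject from the Per-Protocol Set in Section 7.2.

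**Working it through.** **1. Do the vial figures agree with each other?** Section 5.1 gives the formula C33H28O16Na2 and a mass of 726.56 g/mol.

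- Salt, from standard atomic weights: 33 × 12.011 + 28 × 1.008 + 16 × 15.999 + 2 × 22.990 = 726.55 g/mol, as stated to rounding.
- Removing two sodium succinyl groups (C4H3O3Na, 122.055 each): 726.55 − 244.11 = 482.44 g/mol for silibinin. Ratio 482.44 / 726.55 = 0.664.
- 528.5 × 0.664 = 350.9 mg (stated 350). 476 × 0.664 = 316.1 mg (stated 315).
- Assay ratio: 528.5 / 476 = 1.110 and 350 / 315 = 1.111.

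The figures describe one content, expressed by substance and by assay. They do not contradict each other.

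**2. Bag concentration.** Concentration = 4 × (mg per vial) / 500 mL.

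- 350 mg: 1,400 / 500 = 2.80 mg/mL
- 315 mg: 1,260 / 500 = 2.52 mg/mL
- 528.5 mg: 2,114 / 500 = 4.23 mg/mL

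**3. Volume for the same written dose.** Volume = (mg/kg × kg) / concentration. The documents give no body weight, so 50, 70 and 100 kg are assumed. The loading dose is assumed to come from the same bag, because Section 5.1.1 describes only one preparation.

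| Dose | Weight | 350 mg | 315 mg | 528.5 mg |
|---|---|---|---|---|
| Loading, 5 mg/kg | 50 kg | 89 mL | 99 mL | 59 mL |
| Loading, 5 mg/kg | 70 kg | 125 mL | 139 mL | 83 mL |
| Loading, 5 mg/kg | 100 kg | 179 mL | 198 mL | 118 mL |
| Maintenance, 20 mg/kg per 24 h | 50 kg | 357 mL | 397 mL | 237 mL |
| Maintenance, 20 mg/kg per 24 h | 70 kg | 500 mL | 556 mL | 331 mL |
| Maintenance, 20 mg/kg per 24 h | 100 kg | 714 mL | 794 mL | 473 mL |

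At 70 kg the loading dose is 350 mg, which is 350/350 = 1.00, 350/315 = 1.11 or 350/528.5 = 0.66 vials.

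**4. Ratios, which do not depend on weight.** Between the two silibinin assays, 350 / 315 = 1.11. Salt against silibinin, 528.5 / 350 = 1.51 (DNPH) and 528.5 / 315 = 1.68 (HPLC).

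**5. Which ratios does the wording support?**

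- *Loading dose.* It is labelled silibinin in one place and Legalon SIL in two. If the product name is read as salt mass, the 1.51 and 1.68 ratios apply. On the DNPH scale, a written 5 mg/kg is then 5.0 mg silibinin/kg on the 350 mg figure, 5 × 350/315 = 5.6 on the 315 mg figure, or 5 × 350/528.5 = 3.3 on the salt figure.
- *Maintenance dose.* Wherever a substance is attached to it, that substance is silibinin; elsewhere it is unlabelled. The spread from stated wording is 1.11 (500 against 556 mL at 70 kg). The 331 mL figure arises only if a reader supplies a salt basis for unlabelled text.

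**The case against.** The strongest reply is that Legalon SIL is a product name, not a chemical unit. No section gives a dose in mg/kg of the disodium salt, and the synopsis background gives both doses together as silibinin. Table 1 can be read as naming the product to be infused without changing the unit. This largely stands: the 1.5- to 1.7-fold spread depends on a literal reading that the text permits but does not state. It does nothing to settle 350 against 315 mg, or the missing bag concentration.

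Second, safeguards exist. Training is due as soon as possible, with 24 hours as the outer limit. The primary investigator discusses each case before drug is shipped and speaks with the site daily. Section 2.2 points to the Investigator's Brochure and Section 5.4 to the drug label, and either may carry a conversion figure; neither can be seen here. These points lower the likelihood of harm. They do not repair the protocol text, since no section makes the dose basis part of those calls and the brochure is not among the documents listed as sent to the site.

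Third, one carton at 350 mg per vial supplies 4 × 350 = 1,400 mg, exactly 20 mg/kg at 70 kg, which might hint at the intended basis. The protocol never states this as a rule, and Section 2.2.1, despite its title on dose selection, holds only solution-stability data.

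A reader might also infer more than the documents support. The several vial figures are not conflicting contents (step 1). The number of vials per bag does not vary, because Section 5.1.1 fixes it at four; the ambiguity lies in the volume or rate infused. No inconsistent dosing is reported, including in the interim summary of 50 patients in Section 7.6, and no planned efficacy analysis uses the mg dose, so an effect on the results is not shown.

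**Conclusion.** The concern holds as an internal inconsistency in the dose wording that should be corrected. The basis for converting mg/kg to volume is not fixed, and no bag concentration is given.

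For the loading dose, explicit wording allows a spread of 1.5- to 1.7-fold, provided that the product name is read as salt mass; without that reading the spread is 11%. For maintenance the stated wording supports 11%, and a wider spread needs a salt basis that no passage states. The ratios follow from the vial contents alone. The volumes rest on the assumed weights and on a single bag preparation for both doses.

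The case for acting rests on safety and on giving the overdose, dosing-error and deviation rules something to be measured against. It does not rest on any demonstrated misdosing or bias, and the sample size is unaffected.

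**What to change.** The sponsor should reconcile the dose wording in the synopsis (background and methodology), Table 1, Section 2.2, Section 5.1 and Section 5.1.1 to one named substance and one stated content per vial. Section 5.1.1 should then give the resulting bag concentration in mg/mL. The overdose rule in Section 9.2.5, the dosing-error instruction in Section 5.1.1, and the compliance and major-deviation checks under Sections 7.2 and 7.5.1 should refer to the same basis. Which basis is correct is for the sponsor to determine and is not proposed here.

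The cost is protocol and pharmacy wording. There is no change to design, sample size or analysis. Subjects enrolled before the change should have the basis actually used recorded where site records allow, so that exposure can be reported on one scale.
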